### 7.1.1 Temporary discontinuation

For the Cohorts 11 to 14 (inclusive), temporary delays to the boost doses due to intercurrent illness (i.e., immunization with the boost dose within 1 wk of the scheduled day) are allowed.

## 7.1.2 Rechallenge

Not applicable.

# 7.2 Trial subject discontinuation/withdrawal from the trial

A trial subject may withdraw from the trial at any time at his/her own request, or may be withdrawn at any time at the discretion of the investigator for safety, behavioral, compliance, or administrative reasons.

A trial subject in Cohort 11, 12, or 13 who receives a non-trial SARS-CoV-2 vaccination will be withdrawn from follow-up and discontinued from the BNT162-01 trial.

If the trial subject withdraws consent for data processing, the sponsor may retain and continue to use any data collected before such a withdrawal of consent.

If a trial subject withdraws from the trial, he/she may request destruction of any samples taken and not tested, and the investigator must document sample destruction in the Investigator's Site File (ISF).

If the trial subject withdraws consent or is permanently discontinued from the trial, the trial subject will be permanently discontinued both from IMP administration and from the trial at that time.

BioNTech SE	Clinical Trial Protocol	Page 69 of 113
Confidential	including Amendments Nos. 01 to 09	Version: 13.0
	BNT162-01	Date: 12 JAN 2022

### If possible, permanently discontinued trial subjects will:

- Complete all assessments planned for that visit and for the EoT Visit, if discontinued on a visit day.
- Complete all assessments planned for the EoT Visit, if not discontinued on a visit day.
- Subjects permanently discontinued after the EoT Visit will be asked to complete all assessments planned for the last planned visit for that cohort as per the SoA (see Section 1.3).

## 7.3 Lost to follow-up

A trial subject will be considered lost to follow-up if they repeatedly fail to return for scheduled visits and is unable to be contacted by the trial site.

The following actions must be taken if a trial subject fails to return to the trial site for a required trial visit:

- The trial site must attempt to contact the trial subject and reschedule the missed visit as soon as possible and counsel the trial subject on the importance of maintaining the assigned visit schedule and ascertain whether or not the trial subject wishes to and/or should continue in the trial.
- Before a trial subject is deemed lost to follow-up, the investigator or designee must make every effort to regain contact with the trial subject (where possible, three telephone calls and, if necessary, a certified letter to the trial subject's last known mailing address or local equivalent methods). These contact attempts should be documented in the trial subject's medical record.
- If the trial subject continues to be unreachable, they will be considered to have withdrawn from the trial.

## 7.4 Replacement of permanently discontinued trial subjects

Permanently discontinued trial subjects will be replaced to ensure that the 12 subjects complete the trial as planned up to Visit 3 for each group unless permanently discontinued due to safety issues; in the latter cases, the SRC will decide whether to replace the discontinued trial subjects. Trial subjects permanently discontinued after Visit 3 will not be replaced.

## 8 TRIAL ASSESSMENTS AND PROCEDURES

See the SoA (Section 1.3) for all planned time points for assessments.

Protocol waivers or exemptions are not allowed.

Immediate safety concerns should be discussed with the sponsor immediately upon occurrence or awareness to determine if the trial subject should continue or discontinue IMP administration (i.e., to administer the boost administration for groups with the P/B regimen).

Adherence to the trial protocol requirements, including those specified in the SoA, is essential and required for trial conduct.

All screening evaluations must be completed and reviewed to confirm that potential trial subjects meet all eligibility criteria. The investigator will maintain a screening log to record details of all trial subjects screened and to confirm eligibility or record reasons for screening failure, as applicable.

For the baseline assessments (demographics, medical history), see Section 10.12.

The listed trial assessments and procedures will be updated to reflect the needs of Part B in the planned protocol amendment.

## 8.1 Efficacy assessments

Not applicable.

## 8.2 Safety assessments

Planned time points for all safety assessments are provided in the SoA (Section 1.3).

### 8.2.1 Physical examinations

Complete physical examinations will be performed at screening. Brief physical examinations will be performed at later time points including prior boost immunizations (see the SoA in Section 1.3).

- A complete physical examination will include, at a minimum, assessments of the cardiovascular, respiratory, gastrointestinal, and neurological systems. Height (in cm) will also be measured and recorded during complete physical examinations.
- A brief (symptom-directed) physical examination. The brief physical examination includes an overall health judgment. In-depth physical examinations are required if obvious pathological signs are visible or in the case the subject states any signs or symptoms.

### 8.2.2 Vital signs

Body temperature (in °C), pulse rate, respiratory rate, and blood pressure will be assessed at the times given in the SoA (Section 1.3). Body weight (in kg) will also be measured and recorded.

Blood pressure (systolic/diastolic, in mmHg) and pulse (in bpm) measurements will be assessed while the trial subject is in a supine position/at rest. If available, a completely automated device should be used, otherwise manual techniques can be used. The same method of measurement should be used for the trial subject during the course of the trial.

Blood pressure and pulse measurements should be preceded by at least 5 min of rest for the trial subject in a quiet setting without distractions (e.g., television, cell phones).

Vital signs should be taken before any blood collection.

### 8.2.3 Electrocardiograms

**BioNTech SE** 

Confidential

Standard 12-lead ECGs will be recorded at the times given in the SoA (Section 1.3) using an ECG machine that automatically calculates the heart rate and measures PR, QRS, QT, and corrected QT (QTc; according to Bazett) intervals.

ECGs will be judged by the investigator as clinically significant (yes/no); only the investigator assessment and heart rate will be recorded in the CRF.

### 8.2.4 Clinical laboratory tests

See Section 10.2 for the list of clinical laboratory tests to be performed at the times given in the SoA (Section 1.3).

The investigator must review the laboratory report, document this review with signature and date, and record any clinically relevant changes occurring during the trial in the AE section of the CRF.

All laboratory tests with values considered clinically significantly abnormal during participation in the trial should be repeated until the values return to normal or baseline or are no longer considered clinically significant by the investigator or the sponsor's Medical Monitor.

If such values do not return to normal/baseline within a period of time judged reasonable by the investigator, the etiology should be identified and the sponsor notified.

All protocol-required clinical laboratory tests (see Section 10.2) must be conducted in accordance with the trial site standard.

If laboratory values from non-protocol-specified laboratory assessments performed at the laboratory require a change in trial subject management or are considered clinically significant by the investigator (e.g., SAE, AE or dose modification), then the results must be recorded in the CRF.

### 8.2.5 Drugs of abuse screening

Screening for drugs of abuse (amphetamines, benzodiazepines, barbiturates, cocaine, cannabinoids, opiates, methadone, methamphetamines, phencyclidine, and tricyclic antidepressants) will be performed using a commercially available kit at the times given in the SoA (Section 1.3).

### 8.2.6 Testing for alcohol use

Breath testing for alcohol use will be performed at the times given in the SoA (Section 1.3).

### 8.2.7 Viral screening (for blood-borne viruses)

The screen will test for: hepatitis B surface antigen, hepatitis B core antibody, hepatitis C antibodies, and HIV-1 and HIV-2 antibodies. For SARS-CoV-2 testing, see Section 8.2.10.

### 8.2.8 Subject diaries

Trial subjects will be given subject diaries at Visit 1 and be asked to record any reactions between visits, solicited local reactions at the injection site (pain, tenderness,

erythema/redness, induration/swelling) and solicited systemic reactions (nausea, vomiting, diarrhea, headache, fatigue, myalgia, arthralgia, chills, loss of appetite, malaise, and fever [i.e.,  $\geq$ 38°C]).

Subject diaries may include App-supported electronic documentation in compliance with the applicable data protection regulations.

Trial site personnel will collect subject diaries at the visits given in the SoA (Section 1.3).

### 8.2.9 Assessment of local reactions

Local reactions after IM immunization will be assessed by the investigator at the times given in the SoA (Section 1.3). This information will be used to validate the solicited assessment of local reactions in the patient diary and potentially support AE reporting.

Local reactions (both investigator assessed and solicited in the subject diaries) will be graded using criteria based on the guidance given in US FDA Guidance for Industry "Toxicity Grading Scale for Healthy Adult and Adolescent Volunteers Enrolled in Preventive Vaccine Clinical Trials" for "Local Reaction to Injectable Products" (see the section "Assessment of intensity" in Section 10.3.1.11).

### 8.2.10 SARS-CoV-2 testing

SARS-CoV-2 testing (PCR-based and antibody-based) will be performed at the time points provided in the SoA (Section 1.3).

This includes PCR-based testing for SARS-CoV-2 as an eligibility criterion and blood draws for anti-SARS-CoV-2 antibody testing as baseline reference for immunogenicity analysis.

If required, this reference will allow the discrimination between vaccinated and infected subjects.

The screen for SARS-CoV-2 by PCR-based test using oral swipe sample can be performed by either a central laboratory or a "point of care" device at the trial site.

- If a central laboratory is used: Only the SARS-CoV-2 status will be tested and no further data will be generated.
- If a point of care device is used: The most commonly used devices come with predefined test panels that test for a range of pathogens and not just for SARS-CoV-2. Thus, inevitably and automatically, incidental data for the pathogens other than SARS-CoV-2 will be generated when using such devices. Since this incidental data is not required by this trial, only the results for SARS-CoV-2 will be recorded in the CRF, analyzed, and reported as described in this protocol. If a test result for SARS-CoV-2 or another pathogen must be reported to relevant authorities, this notification will be done by the trial site.

Clinical Trial Protocol including Amendments Nos. 01 to 09 BNT162-01 Page 73 of 113 Version: 13.0 Date: 12 JAN 2022

The anti-SARS-CoV-2 antibody testing will be performed with a commercially available antibody test. In case this commercial antibody test can, discriminate between vaccine-specific and infection-specific antibody responses (based on the antigens used), it will be used to test subjects who may have experienced enhanced respiratory disease or progression of flu-like symptomatology, such as non-resolution of the symptoms after 7 d, symptom kinetics that are inconsistent with a relationship to RNA immunization, as might be expected with a COVID-19 disease (see Section 6.6.3).

In these cases, ad hoc anti-SARS-CoV-2 antibody testing will be performed to test for the development and presence of SARS-CoV-2-specific antibodies, ideally at approximately 14 d and 28 d after the last immunization with the BNT162 candidate vaccine. This data will be used to evaluate the development and progression of an antibody response allowing the diagnosis of a manifest infection.

In case this commercially available test cannot discriminate between vaccine-specific and infection-specific antibody responses, the same kind of analysis will be performed with a custom-made assay specifically developed by the CRO.

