# 9 STATISTICAL CONSIDERATIONS

# 9.1 Statistical hypotheses

There is no formal statistical hypothesis under test.

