# 9.2 Sample size determination

No formal sample size calculations have been performed.

For Part A, the inclusion of 12 subjects per group is considered to be adequate for a safety assessment of each vaccine per dose level. The probability to observe a particular TEAE with incidence of 15% at least once in 12 subjects per group is 85.8%.

For the expansion cohorts the probability to observe a particular TEAE with incidence of 5% at least once in 30 and 90 subjects per group, respectively, is 78.5% and 99.0% respectively (see Table 10).

Number of subjects	TEAE incidence	Probability to observe a particular TEAE at least once
12	15%	85.8%
30	15%	99.2%
	10%	95.8%
	5%	78.5%
90	15%	>99.9%
	10%	>99.9%
	5%	99.0%

Table 10: Probability to observe a particular TEAE at least once

TEAE = treatment-emergent adverse event.

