#### AEs of proven COVID-19 disease:

Any case of proven COVID-19 disease occurring till the last FU Visit should be reported as an SAE/AE. AEs which are rated as "moderate" or "severe" (according to the criteria provided in Section 10.3.1.7) will need to be reported as an SAE. If none of the other SAE definitions are deemed suitable, then the SAE criterion of being a "medically important event" should be applied (according to the definitions provided in Section 10.3.1.4). An SAE form should be completed, including follow-up information, as detailed in Section 10.3.1.10 such that an SAE report and narrative can be prepared and distributed.

BioNTech SE	Clinical Trial Protocol	Page 98 of 113
Confidential	including Amendments Nos. 01 to 09	Version: 13.0
	BNT162-01	Date: 12 JAN 2022

All mild cases of proven COVID-19 cases which do not correspond to seriousness criteria will be reported as AEs in the CRF.

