#### AEs

The number and percentage of subjects reporting at least one AE and the number of AEs will be summarized for the above defined time interval 'After Day 28 after boost or after prime (if no boost)' and the following AE types:

- Any AE
- Related AE
- Grade >=3 AE

- Related grade >=3 AE
- AEs with dose limiting toxicity (DLT)
- Any serious adverse event (SAE)
- Related SAE
- Deaths
- Any AEs linked to confirmed COVID-19 cases (defined as AEDECOD = 'COVID-19')

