## 6.5. Secondary Analyses

Hereinafter, the secondary analyses for Part A are described.

Secondary endpoints are functional antibody responses, fold increase in functional antibody titers and the number of subjects with seroconversion. All secondary analyses will be performed using the IMM and possibly additionally the IMMPP population, see section 5.1.

All secondary analysis endpoints will be summarized by group (i.e. by vaccine type and cohort) and all cohorts combined for each type (cohort-total).

The functional antibody response will be assessed at the time points indicated in the tables 6, 7, 8 and 9 of the protocol.

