#### 6.7.5. Further Safety Data

Physical examination, drugs of abuse, alcohol use, viral screening and the SARS-CoV-2 testing will be listed.

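### The functional antibody summaries state no handling of SARS-CoV-2 infection, so late titers and apparent waning mix vaccine response with infection

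*Protocol*

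**What the plan says.** **What is collected.** Protocol 8.2.10 takes an antibody sample at Visit 0 as a reference for immunogenicity: "If required, this reference will allow the discrimination between vaccinated and infected subjects". Protocol 10.3.1.9 adds: "Any case of proven COVID-19 disease occurring till the last FU Visit should be reported as an SAE/AE". Exclusion criteria 11, 25 and 26 cover a recent positive PCR, current symptoms and recent contact. A positive antibody test is not an exclusion, and Protocol 8.10 defines seroconversion for sera that are already positive before immunization.

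**What is analysed.** SAP 6.5: "All secondary analyses will be performed using the IMM and possibly additionally the IMMPP population". Under SAP 5.1, IMM needs one dose and one post-baseline functional titer. The per-protocol version (IMMPP) removes only major deviations as judged by the clinician. The examples in SAP 5.2 do not name infection during follow-up, and SAP 6.1.1 makes use of IMMPP optional. SAP 6.5.1 to 6.5.3 summarize titer, fold increase and seroconversion at all time points. SAP 5.3 plans no subgroups beyond optional age totals.

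**Where infection appears.** SAP 6.7.5: "Physical examination, drugs of abuse, alcohol use, viral screening and the SARS-CoV-2 testing will be listed". SAP 6.4.3 counts adverse events with preferred term COVID-19, but only in the interval after Day 28 following the boost (or the prime, if there was no boost).

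**The neighbouring rule.** SAP 6.1 excludes data assessed after a non-trial vaccination from every analysis.

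**The concern.** The trial ran during a pandemic. Functional titers are listed secondary endpoints to Day 184, and Protocol Table 8 schedules immunogenicity draws to Day 730 in Cohorts 11 to 13, whose rationale in Protocol 4.2 includes long-term monitoring of the immune response. Infection, like a further vaccination, is an exposure outside the trial that can raise the titer. The SAP has a rule for one and is silent on the other.

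What is at stake is how the late geometric mean titer (GMT), geometric mean fold rise (GMFR) and seroconversion figures are read. A reader will take them as persistence of the vaccine response, yet they would carry an unknown contribution from infection. That contribution can differ between cohorts enrolled at different times, and SAP 6.5 also pools cohorts into a total per vaccine.

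**Working it through.** **1. The plan's own figures.** The documents give no figure for infection or titers. The only probabilities are those in Protocol 9.2, for seeing an adverse event at least once, 1 − (1 − q)^n:

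- n = 12, q = 15%: 1 − 0.85^12 = 0.858
- n = 30, q = 5%: 1 − 0.95^30 = 0.785
- n = 90, q = 5%: 1 − 0.95^90 = 0.990

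These match the stated 85.8%, 78.5% and 99.0%. They do not bear on titers, but the same formula gives the chance that a cohort contains at least one infected subject. At an assumed infection rate of 5% it is 46.0% (n = 12), 78.5% (n = 30) and 99.0% (n = 90). At 10% it is 71.8%, 95.8% and above 99.9%.

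**2. Infection after baseline.** SAP 6.1.1 defines GMT as the back-transformed mean of log titers. If a share p of the samples at a visit has titers r times what they would otherwise have been, the mean log titer rises by p × log r and GMT is multiplied by r^p. Baseline is unaffected, so GMFR takes the same factor. Both p and r are assumed.

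| Share infected | r = 4 | r = 10 | r = 30 |
|---|---|---|---|
| 1 of 12 | 1.12 | 1.21 | 1.33 |
| 10% | 1.15 | 1.26 | 1.41 |
| 20% | 1.32 | 1.58 | 1.97 |

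**3. Apparent waning.** If the true fall from peak to a late visit is 4-fold and infection affects only the late visit, the observed fall is 4 / r^p.

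| Share infected | r = 4 | r = 10 | r = 30 |
|---|---|---|---|
| 10% | 3.48 | 3.18 | 2.85 |
| 20% | 3.03 | 2.52 | 2.03 |

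**4. Seroconversion.** Infection after baseline can only leave a subject's status unchanged or turn it positive. One such subject moves the proportion by at most 1/12 = 8.3, 1/30 = 3.3 or 1/90 = 1.1 percentage points.

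**5. Infection before baseline.** Let affected subjects have baseline titers B times, and post-dose titers R times, those of naive subjects. GMFR is then multiplied by (R/B)^p. With p = 10% (all values assumed):

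- B = 4, R = 1: 0.87
- B = 10, R = 1: 0.79
- B = 10, R = 4: 0.91
- B = 4, R = 10: 1.10

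The direction depends on whether prior infection raises the baseline or the vaccine response by more.

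**The case against.** **Retaining infected subjects may be deliberate.** Counting titers whatever happens is a legitimate treatment-policy choice. This stands as an argument against forbidding it. But the SAP does not state the choice.

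**The vaccination rule is not a pure parallel.** Subjects who receive a non-trial SARS-CoV-2 vaccine are discontinued (Protocol 6.5 and 7.2), and a Table 8 footnote stops their immunogenicity sampling, so the SAP 6.1 rule partly follows from conduct. That weakens the contrast without removing it. The sampling stop is written for Cohorts 11 to 13, whereas the SAP rule covers all cohorts and all data, including titers.

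**Nothing planned was dropped.** A reader might infer that the SAP abandoned a protocol analysis and that Appendix 1 should have recorded it. The documents do not support this. The Protocol 8.2.10 wording is conditional, and Protocol 9.4.3 plans only summaries by group.

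**Baseline status is partly handled.** Fold increase uses each subject's own baseline, and Protocol 8.10 has a rule for seropositive sera. This stands, so a reader should not infer that prior infection necessarily lowers GMFR. The tables still mix primed with naive subjects, and raw GMT has no adjustment.

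**The latest visits may hold few subjects.** The listed secondary endpoints stop at Day 184. Days 365 to 730 enter through Table 8 and the all-time-points wording, and Protocol 4.4 foresees that no subjects may remain for the two-year follow-up. This stands; where few remain, each infected subject weighs more.

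**The trial is descriptive.** Protocol 9.1: "There is no formal statistical hypothesis under test". Titers, adverse events and SARS-CoV-2 tests are all listed, so affected subjects can be traced. But the listings do not correct the summary tables and line plots.

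**Conclusion.** The point holds. As written, SAP 6.5 puts samples taken after SARS-CoV-2 infection into the GMT, GMFR and seroconversion summaries without stating a strategy, although the data needed to show their influence are collected. The stronger part is infection after baseline, which pushes late titers up and makes waning look smaller. The weaker part is prior infection, which mixes two kinds of responder and shifts GMFR in a direction that cannot be predicted.

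The size is illustrative only: late GMT and GMFR inflated by 15% to 41% at an assumed 10% infected, and by 32% to 97% at an assumed 20%, for a 4- to 30-fold effect. A reader might take these as estimates of actual bias. They are not, since the documents supply neither the infection rate nor the effect on titer. Nor do the documents support making an infection-excluded set the main analysis: censoring at infection may itself select on response, and in an open-label trial with permitted snapshot analyses a late switch of the main set would be open to challenge.

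The separate biomarker SAP does not close the gap. It covers exploratory endpoints, and functional titers are secondary endpoints under this SAP.

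**What to change.** In SAP 6.5:

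1. State the strategy for SARS-CoV-2 infection explicitly.
2. Keep the all-samples IMM summary.
3. Add a pre-specified parallel set of GMT, GMFR and seroconversion tables that excludes samples taken from the onset of confirmed COVID-19. Identify cases by AEDECOD = COVID-19 at any time after the first dose, not only in the after-Day-28 interval of SAP 6.4.3.
4. Show the summaries by Visit 0 anti-SARS-CoV-2 antibody status.
5. Give the number of subjects excluded at each visit.

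**Cost.** SAP wording and additional runs of existing tables, from data already collected. No new visits or samples are needed.

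**Downsides.** The parallel tables will have fewer subjects at late visits. If low responders are infected more often, excluding their later samples raises the remaining GMT, which is why both versions should be shown. Asymptomatic infection stays undetected: scheduled antibody testing is at Visit 0 only, and later testing under Protocol 8.2.10 is ad hoc and prompted by symptoms.
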